Randomisation	
Randomisation with allocation concealment will utilise a centralised, web-based system (Sealed Envelope Ltd, London, UK). Participants will be randomised on the day of consent in a 1:1 ratio stratified by centre, and presentation (acute versus chronic coronary syndrome).

Trial Interventions	
Study participants will be randomised in a 1:1 manner to either Revascularisation by PCI or Revascularisation by CABG

Outcomes	
Primary Outcome: Survival time from all-cause mortality and cardiovascular hospitalisation.
 
Secondary Outcomes: 1. Overall survival time (all-cause). 2. Cardiovascular survival time 3. Time to first cardiovascular hospitalisation. 4. Time to first heart failure hospitalisation. 5. Time to first non-procedural myocardial infarction 6. Time to first revascularisation following assigned treatment with PCI or CABG. 7. Time to stroke. 8. Days Alive and Out of Hospital at 90-and 365-days. 9. The number of total (first and recurrent) cardiovascular hospitalisations and heart failure hospitalisations. 10. Kansas City Cardiomyopathy Questionnaire (KCCQ) at baseline, discharge, 3 months, 6 months and then every 6 months until end of trial follow-up. 11. Seattle Angina Questionnaire-7 (SAQ-7) at baseline, discharge, 3 months, 6 months, and then every 6 months until end of trial follow-up. 12. Quality of life measured by the EQ-5D-5L questionnaire at baseline, 3 months, 6 months and annually until end of trial follow-up.
 
Serious Adverse events within 30 days of PCI or CABG: 1. Stroke 2. New onset end-stage renal failure defined as requiring dialysis. 3. Unplanned mechanical circulatory support (IABP, Impella, VA ECMO). 4. Major bleeding requiring reoperation or re-hospitalisation. 5. Major vascular complication requiring interventional radiology or surgical intervention. 6. All-cause mortality.

Planned Size of Sample (if applicable)	
Using a time-to-event analysis to detect a Hazard Ratio of 0.7 for the primary outcome with a 1:1 allocation ratio, 90% power, and a 2-sided alpha value of 0.05, a total of 414 events will be required, enrolling 630 participants (n=315 in each arm).

Follow up duration	A median follow-up of up to 5 years (and minimum 4 years follow-up) post randomisation.
Planned Study Period	101 months starting from 1 st October 2023.

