1.16 SIZE OF SAMPLE

STICH3-BCIS4 is a superiority trial powered for the primary outcome of survival time from cardiovascular hospitalisation and all-cause mortality. Using a time-to-event analysis to detect a HR of 0.7 with a 1:1 allocation ratio, 90% power, and a 2-sided alpha value of 0.05, a total of 414 events are required. Participants will receive a minimum of 4 years follow-up and 630 participants (n=315 in each arm) will be randomised in the UK.

The sample size is based on the following assumptions. **1.** A minimum clinically important treatment effect HR for CABG vs. PCI of 0.7 that is written within the range of treatment effects (0.63 to 0.74) observed in previous pragmatic RCTs of CABG versus PCI that have changed clinical practice (20-22). The proposed effect size was chosen as stakeholders felt that a large benefit would be required to convince clinicians of the benefits of more invasive treatment (CABG) in this high-risk population. **2.** Frequency of death or cardiovascular hospitalisation of 70% at 5 years in the PCI arm, from HES. To

calibrate this outcome, we compared the frequency of death or *heart failure* hospitalisation at 5 years in the STICH-1 matched HES cohort (42%) to event rates in both REVIVED and STICH trials (see Figure 1, from reference (8)). As heart failure hospitalisation is underestimated in HES data, the expected outcome frequencies are consistent. Coding for CV hospitalisation is more accurate and is included in the primary outcome for STICH3-BCIS4. **3.** A total study period of 89 months. **4.** An expected crossover rate of 8% typical for CABG vs. PCI trials; range 7-9%. (6, 7). **5.** Zero attrition due to the use of HES / Office for National Statistics (ONS) data for the primary outcome.

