1.17.2 Secondary Effectiveness Outcomes

- 1.** Overall survival time, defined in whole days measured as time from randomisation until date of death from any cause. Participants who withdraw or are lost to follow-up will be censored at the date last known to be alive. Participants not having an event at the time of the analysis will be censored at the last date known to be alive.
- 2.** Cardiovascular survival time, defined in whole days measured as time from randomisation until date of death from cardiovascular cause. Participants who withdraw or are lost to follow-up will be censored at the date last known to be alive. Participants not having an event at the time of the analysis will be censored at the last date known to be alive. Participants who die from other causes will be censored at date of death.
- 3.** Time until cardiovascular hospitalisation, defined in whole days measured as time from randomisation until cardiovascular hospitalisation. All other participants will be censored at last known follow-up assessment having not had a cardiovascular hospitalisation.

4. Time until heart failure hospitalisation, defined in whole days measured as time from randomisation until heart failure hospitalisation. All other participants will be censored at last known follow-up assessment having not had a heart failure hospitalisation.
5. Time until non-procedural myocardial infarction, defined in whole days measured as time from randomisation until non-procedural myocardial infarction. All other participants will be censored at last known follow-up assessment having not had a non-procedural myocardial infarction.
6. Time until revascularisation other than assigned treatment, defined in whole days measured as time from randomisation until revascularisation. All other participants will be censored at last known follow-up assessment having not had a revascularisation.
7. Time until stroke, defined in whole days measured as time from randomisation until date of stroke. All other participants will be censored at last known follow-up assessment having not had a stroke.
8. Days Alive and Out of Hospital at 90 and 365 days, defined in whole days measured as a continuous variable, calculated as last known date to be alive, minus discharge date following assigned treatment, minus all episodes of hospitalisation (discharge date minus admission date).

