1.33 EXPECTED SERIOUS ADVERSE EVENTS

The risk of intervention is not negligible. In the STICH trial, participants with ischaemic left ventricular dysfunction undergoing CABG had 5% mortality at 30 days post-surgery. In contrast, the peri-procedural risk of death following PCI should be less, although the overall burden of SAEs may be similar. In the SYNTAX trial (22) for example, the rate of Major Adverse Events at 30 days was the same in both CABG and PCI groups (only 7% of participant in this trial had iLVSD). However, with time, recurrent symptoms and repeat revascularisation are typically higher in the PCI treated patients, meaning that freedom from death or revascularisation is lower. This is evident in the Kaplan Meier curves in Figure 3, where the CABG curve (blue) is initially lower, but then crosses the PCI curve (red) after 3-6 months.

[figure not shown]

Figure 3 Freedom from death or cardiovascular hospitalisation in people with heart failure undergoing CABG or complex PCI in England 2013-2018, or matched to the STICH cohort (8)

However, other trials have identified important differences in early expected adverse events following both PCI or CABG (32). These include the risk of stroke, severe acute kidney injury (AKI), unplanned mechanical circulatory support for low cardiac output, major bleeding requiring intervention, or vascular complications requiring intervention. Along with early deaths, this information may be important for future patients with iLVSD who are deciding whether to undergo PCI or CABG. These early events may also be used by governance committees to establish whether there are any clinical differences in the number of these events versus expected event rates in normal practice. For this reason, we propose to collect the following SAEs occurring within 30 days of the date of surgery or the date of the first index PCI procedure, for review by governance committees.

1. Stroke
2. New onset end-stage renal failure defined as requiring dialysis
3. Unplanned mechanical circulatory support (IABP, Impella, VA ECMO)
4. Major bleeding requiring reoperation or re-hospitalisation
5. Major vascular complication requiring interventional radiology or surgical intervention
6. All-cause mortality

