1.43 ANALYSIS POPULATION

The primary analysis will be based on ITT principles with the analysis population consisting of all participants who are randomised and compared in the groups to which they were allocated regardless of treatment being received. The per-protocol (PP) population will consist of all participants who underwent revascularisation as randomised, excluding patients who had a major protocol deviation e.g., patients who crossed over, had their allocated treatment changed or discontinued by the treating physician at any time, or withdrew consent.

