1.47 SECONDARY AND TERTIARY OUTCOMES AND SAFETY ANALYSES

Details of the analysis of the secondary outcome measures will be written in the SAP as described above and will follow the same principles as the primary outcome analysis with the exception of outcomes with potentially missing follow-up observations (e.g., PROMS) where a complete case analysis approach will be followed. Secondary outcomes will be reported similarly to the primary outcome using appropriate methodology, point estimates and confidence intervals to compare randomised groups; time to event outcomes using log-rank Kaplan-Meier and proportional hazards models, binary outcomes using logistic regression, continuous outcomes using linear regression or where not normally distributed using appropriate nonparametric methods.

Serious adverse event reporting is described in earlier sections and is largely for safety and ethics monitoring during the trial accrual and follow-up periods prior to statistical analysis taking place. AEs that meet the criteria for reporting as described above will be reported descriptively and summarised between groups based on the safety population (e.g., assigned to groups only if treated and according to treatment received).

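### Secondary outcome 6 (revascularisation) is worded two ways, and under section 1.17.2 a crossover procedure counts as an event

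*Protocol*

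**What the plan says.** The Study Summary lists secondary outcome 6 as "Time to first revascularisation following assigned treatment with PCI or CABG". It gives no time origin.

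Section 1.17.2, item 6, defines what should be the same outcome as "Time until revascularisation other than assigned treatment, defined in whole days measured as time from randomisation until revascularisation". Its censoring rule is "All other participants will be censored at last known follow-up assessment having not had a revascularisation".

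Four other places bear on how the difference plays out:

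- Section 1.16 assumes "An expected crossover rate of 8% typical for CABG vs. PCI trials; range 7-9" (per cent) and states that "630 participants (n=315 in each arm) will be randomised in the UK". It does not say how crossover divides between the arms, or whether 8% is an overall or a per-arm figure.
- Section 1.43 analyses participants by allocation, "compared in the groups to which they were allocated regardless of treatment being received", and section 1.47 carries the same principles to the secondary outcomes, with "time to event outcomes using log-rank Kaplan-Meier and proportional hazards models".
- Sections 1.43 and 1.62 both give crossover as an example of a protocol deviation.
- Section 1.33 expects that "recurrent symptoms and repeat revascularisation are typically higher in the PCI treated patients", but gives no rate.

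**The concern.** An outcome meant to capture the durability of the first revascularisation should not also record failure to receive the allocated procedure. Take a participant allocated CABG whose first and only procedure is PCI. Nothing has been repeated. Under section 1.17.2 that PCI is a revascularisation other than the assigned one, so the participant has an event. Under the Summary there was no assigned treatment for a revascularisation to follow, so there is no event. Because the analysis is by allocated group, the procedure enters the comparison in the CABG arm. It also enters early, since it normally stands in for the index procedure.

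This is the outcome on which the protocol itself expects PCI to do worse. If the section 1.17.2 wording is followed, the reported effect mixes repeat revascularisation with non-adherence. The choice between the two wordings should not be left until outcome data are available by arm.

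**Working it through.** **The texts side by side, for a participant in either arm**

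| Course of events | Study Summary | Section 1.17.2, item 6 |
|---|---|---|
| Allocated procedure, nothing further | no event | no event |
| Allocated procedure, later unplanned repeat | event | event, if the wording means any procedure apart from the index one |
| Other procedure instead of the allocated one, nothing further | no event | event |

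The third row is the main difference. The second row holds only on one reading of section 1.17.2. If its words mean *by the other type of procedure*, a repeat PCI in the PCI arm is not counted, while a PCI in the CABG arm is.

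**Inputs**

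- From section 1.16: n = 315 per arm; crossover c = 8% (range 7 to 9%).
- Assumed, because the protocol gives no rates: true repeat revascularisation r of 15% in PCI and 7% in CABG, varied from 10% v 5% to 20% v 10%.
- Assumed: the split of crossover by arm.

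The protocol states no figure for this outcome, so there is none to reproduce.

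**Number of crossover events.** 0.08 × 315 = 25.2 per arm if balanced, so about 50 of 630. At 7% and 9% it is 22.1 and 28.4 per arm.

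**Only repeats counted.**

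- Ignoring crossover: 315 × 0.15 = 47.2 v 315 × 0.07 = 22.1; ratio 0.07/0.15 = 0.47.
- Giving crossovers the repeat rate of the treatment they received, 8% in each arm: PCI 0.92 × 0.15 + 0.08 × 0.07 = 0.1436 (45.2 events); CABG 0.92 × 0.07 + 0.08 × 0.15 = 0.0764 (24.1 events); ratio 0.53.

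**Crossover counted as an event.** Proportion with an event = c + (1 − c) × r.

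- PCI with 8% crossover: 0.08 + 0.92 × 0.15 = 0.2180 (68.7 events).
- CABG with 8% crossover: 0.08 + 0.92 × 0.07 = 0.1444 (45.5 events).

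| Crossover | PCI events | CABG events | Risk ratio |
|---|---|---|---|
| 8% in each arm | 68.7 | 45.5 | 0.1444/0.2180 = 0.66 |
| 8% in CABG arm only | 47.2 | 45.5 | 0.1444/0.15 = 0.96 |
| 8% in PCI arm only | 68.7 | 22.1 | 0.07/0.2180 = 0.32 |

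**Sensitivity to the assumed repeat rates.** For 10% v 5% and 20% v 10% the ratio ignoring crossover is 0.50.

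- 8% in each arm: 0.126/0.172 = 0.73 and 0.172/0.264 = 0.65.
- CABG arm only: 0.126/0.10 = 1.26 and 0.172/0.20 = 0.86.
- PCI arm only: 0.05/0.172 = 0.29 and 0.10/0.264 = 0.38.

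The one-arm cases put 8% in one arm and none in the other, which is 4% of the trial.

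**The case against.** A harmonising reading exists. If the section 1.17.2 wording means any revascularisation apart from the index procedure, the two texts name the same event for everyone who receives the allocated procedure, about 92% of participants on the protocol's assumption. This stands. A reader might infer that the protocol defines two wholly different outcomes, and the documents do not support that. The disagreement is mainly about how crossovers are scored.

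A reader might also infer that the section 1.17.2 wording biases the result towards no difference, or reverses it. That does not follow either. Balanced crossover only dilutes the contrast. A ratio near or above 1 needs crossover concentrated in the CABG arm, and above 1 in the cases worked here also needs low repeat rates. Crossover mainly from the PCI arm would exaggerate CABG's benefit. The split and the repeat rates are not in the protocol.

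The third tempting reading is that repeat PCI in the PCI arm is excluded by design. The words allow it, but it sits badly with the Summary, which covers revascularisation after either treatment, and with section 1.33. It is an ambiguity to close, not a stated rule.

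Finally, sections 1.31 and 1.47 leave HES codes and analysis details to the SAP, so silence there on index or staged procedures is no fault of the protocol. But codes cannot settle which of two stated events is meant. The outcome is also secondary: the primary outcome and the sample size are untouched.

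**Conclusion.** The inconsistency is real and no section resolves it. Following section 1.17.2 as written scores crossover procedures as outcome events, about 25 per arm if the protocol's 8% is balanced, while the Summary scores none of them.

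The effect on the estimate is conditional. Under the assumed rates of 15% v 7%, a risk ratio of 0.47 to 0.53 for true repeats becomes 0.66 with balanced crossover, 0.96 with crossover in the CABG arm only, and 0.32 with crossover in the PCI arm only. These are illustrations that rest on assumed repeat rates and splits, not predictions. What is firm is that the size and direction of the distortion would be set by adherence, not by the durability of either procedure. It should be corrected before outcome data are analysed by arm.

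**What to change.** Use one definition in the Study Summary and in section 1.17.2:

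- **Event:** the first unplanned PCI or CABG, of either type, after the first revascularisation actually performed. Planned PCI stages documented at the first procedure count as part of that first revascularisation. Naming both types rules out the other-type reading.
- **Time origin and groups:** time from randomisation, analysed by randomised group.
- **Never revascularised:** state how these participants are handled.
- **Crossover:** report separately by arm, as adherence.

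Other definitions could be defended. What is needed is that both places state the same event and an explicit rule for crossover.

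The cost is mainly wording in the protocol, matched in the SAP. One data item needs checking. Section 1.27.2 requires the intention to stage to be documented at the first PCI, but does not name it among the details to be recorded in the CRF. Later outcomes come from routine data, so the eCRF should capture it.

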1.27 ALLOCATED TREATMENT

Revascularisation appropriateness and feasibility will be confirmed by the local Heart Team (a minimum of an interventional cardiologist and a cardiac surgeon). Revascularisation should be performed as soon as dictated by clinical urgency but no more than 18 weeks (+/- 28 days) from randomisation for elective cases or 6 weeks from randomisation for urgent/ACS cases (+/- 28 days).

Complete revascularisation of all viable myocardium is the goal for all patients. Revascularisation will be attempted on/for significant lesions in major coronary vessels/side branches as planned by the local Heart Team, with the general recommendation of stenotic/occluded vessels with diameter >1.5mm. As per contemporary ESC treatment guidelines, physiological or non-invasive functional confirmation of haemodynamic severity should be sought in any vessel that has <90% stenosis. As a measure of process, and to estimate completeness of revascularisation, the British Cardiovascular Intervention Society Jeopardy Score (BCIS-JS) will be calculated at baseline and after final stage PCI or CABG using the www.BCIS-JS.com calculator.

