1.31 OUTCOMES POST RANDOMISATION

Trained staff will use the Investigator portal in the ResearchApp™ (Healthbit®) to collect the following:

1. Baseline data will include patient demographics, such as age, sex, and ethnicity, as well as long term conditions and pre-operative investigations, severity of cardiac disease, risk scores (BCIS Jeopardy Scores. EuroSCORE II), revascularisation procedures, completeness of revascularisation, defined as change in BCIS-JS from baseline.
2. Mortality will be ascertained in UK participants through ONS data access request.
3. Outcomes until hospital discharge:
 - a) Unplanned mechanical circulatory support defined as the need for IABP, ventricular assist device or ECMO postoperatively.
 - b) New onset renal failure requiring renal replacement therapy (excluding dialysis during cardiopulmonary bypass (CPB)).
 - c) New focal neurological deficit (stroke) lasting more than 24 hours confirmed by clinical assessment and brain imaging.
 - d) Infection: defined as septic shock with positive blood cultures; pneumonia defined as autopsy diagnosis or roentgenographic infiltrate and at least two of the following three criteria: fever, leukocytosis, and positive septum culture; and/or deep sternal or leg wound infection requiring intravenous antibiotics and/or surgical debridement.
 - e) Bleeding requiring surgical or percutaneous intervention.
 - f) Length of stay in the Intensive Care Unit (ICU) readmissions and hospital (time to discharge from acute care after index hospitalisation; this includes time to discharge from satellite acute care units) and Days Alive and Out of Hospital at 6 months.
4. Clinical effectiveness and adverse outcomes post discharge will be ascertained using HES data obtained from NHS Digital using Primary Diagnostic International Classification of Diseases, Tenth Revision (ICD10) codes as previously described (8). ONS data will be used for ascertainment of mortality. NHS numbers will be used to submit ONS/NHS Digital data access requests by the LCTU after last participant/last visit in the UK arm.

For the primary outcome, the following HES codes will be used:

- a) All-cause mortality (ICD10): (dismeth = 4) OR (a linked record in ONS death registry). Follow-up begins the day after operation date.

- b) Cardiovascular hospitalisation and hospitalisation admission after the index admission with ICD10: I00 to I99 (which encompass all the cardiovascular diagnoses) as the *primary* diagnostic code.

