1.50 MISSING VALUES

The primary outcome measures time until first event or censors at last follow-up therefore by definition there will not be any missing data. Other data adjusted for in the primary outcome analysis is a requirement of randomisation and therefore will not be missing. The use of routine and ONS data ensures we will have good long-term follow-up rates and early censoring due to loss to follow-up should be minimal at most and not expected at all. Analysis of non-time-to-event secondary outcomes like PROMs will be by complete case, the extent of missing data will be described.

HEALTH ECONOMIC EVALUATION

Evidence has shown that coronary heart disease cost £1.7 billion to the UK healthcare service, £2.4 billion in informal care, and £2.9 billion in productivity loss (34). The health economic evaluation will determine cost-effectiveness of CABG, compared with PCI, from the perspective of the UK NHS and personal social services, and the patient in line with the National Institute for Health and Care Excellence (NICE) guidance for health technology evaluation (35).

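### The Days Alive and Out of Hospital formula does not yield a 90- or 365-day outcome: it has no cut-off, an origin that depends on treatment, and no value for some randomised participants

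*Protocol*

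**What the plan says.** The outcome is introduced in Protocol 1.17.2, item 8, as "Days Alive and Out of Hospital at 90 and 365 days, defined in whole days measured as a continuous variable". The same sentence gives the calculation: "calculated as last known date to be alive, minus discharge date following assigned treatment, minus all episodes of hospitalisation". The last term is a bracketed difference of dates for each episode, "minus all episodes of hospitalisation (discharge date minus admission date", and the index episode is not excluded from it. The Study Summary also gives 90 and 365 days. Section 1.31, item 3f, lists "Days Alive and Out of Hospital at 6 months", under a list of outcomes up to hospital discharge.

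Three other provisions bear on who receives a value. Section 1.43 defines the intention-to-treat population as "all participants who are randomised and compared in the groups to which they were allocated regardless of treatment being received", and 1.47 carries the principles of the primary analysis over to the secondary outcomes, except those with potentially missing follow-up. Section 1.50 states: "Analysis of non-time-to-event secondary outcomes like PROMs will be by complete case, the extent of missing data will be described". Section 1.27 allows the procedure to take place "no more than 18 weeks (+/- 28 days) from randomisation for elective cases".

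**The concern.** The protocol does not leave this definition to the analysis plan. It fixes a formula, and that formula does not produce the outcome it is attached to.

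- **No cut-off.** The 90- and 365-day limits stand only in the name of the outcome.
- **Origin.** The count starts at a post-randomisation date that depends on the treatment, the wait and the length of stay. Staged PCI is permitted (1.27.2, item 7), and the formula does not say which discharge starts the clock.
- **Undefined values.** Anyone without a discharge after the assigned treatment has no starting date.
- **Time points.** 90 and 365 days in two places, 6 months in a third.

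At stake is whether the outcome can show the difference in early hospital time between surgery and PCI, and whether the comparison keeps all randomised participants.

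**Working it through.** The protocol states no DAOH mean, standard deviation or power, so there is no figure to reproduce. The check applies the formula to worked participants.

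**Inputs from the protocol:** 315 per arm, minimum follow-up of 4 years and 8% expected crossover (1.16); elective procedures up to 18 x 7 = 126 days after randomisation, or 154 with the 28-day tolerance (1.27); early mortality after CABG of 5% (1.33), 4% and 3% (1.58.3); 30-day mortality after PCI of 4.8% (1.58.4).

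**Assumptions (the protocol gives no lengths of stay):** index stay 2 to 4 days for PCI and 7 to 14 for CABG, with one 30-day case; procedure on day 14 unless stated; no readmissions; last known alive on day 1,826 (5 years), or day 1,461 (4 years) for the day-126 case.

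**Readings for the 90-day outcome:**
- A, literal: last alive - discharge
- B, capped at day 90 from randomisation: min(last alive, 90) - discharge
- C, 90-day window from discharge: min(last alive - discharge, 90)
- D, days alive and not an inpatient within 90 days of randomisation
- E, the same within 90 days of the procedure

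| Participant | A | B | C | D | E |
|---|---|---|---|---|---|
| PCI, 2-day stay | 1,826 - 16 = 1,810 | 90 - 16 = 74 | 90 | 88 | 88 |
| CABG, 10-day stay | 1,826 - 24 = 1,802 | 90 - 24 = 66 | 90 | 80 | 80 |
| CABG, 30-day stay | 1,826 - 44 = 1,782 | 90 - 44 = 46 | 90 | 60 | 60 |
| CABG on day 126, 10-day stay | 1,461 - 136 = 1,325 | 90 - 136 = -46 | 90 | 90 | 80 |
| CABG, dies in hospital on day 19 | none | none | none | 14 | 0 |
| CABG, 10-day stay, dies at home on day 60 | 60 - 24 = 36 | 36 | 36 | 50 | 36 |

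Column A contains no 90 or 365, so it also serves as the 365-day result. In column B the wait at home is deducted with the stay: the PCI participant loses 16 days although only 2 were spent in hospital. In column C the index stay vanishes.

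**Which episodes are deducted.** If the index episode belongs to the deductions, reading B removes it twice: 74 - 2 = 72 for PCI and 66 - 10 = 56 for CABG, a gap of 16 days where the stays differ by 8. Reading C would then become 88 and 80. The text does not settle this.

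**Size of the arm difference.** Take all early deaths as in hospital and scored 0. The CABG-minus-PCI mean under E is (1 - mC)(90 - LC) - (1 - mP)(90 - LP), where m is early mortality and L the index stay.
- mC = 0.03, LC = 7, mP = 0.048, LP = 2: 0.97 x 83 - 0.952 x 88 = 80.5 - 83.8 = -3.3 days
- mC = 0.05, LC = 14, mP = 0.048, LP = 4: 0.95 x 76 - 0.952 x 86 = 72.2 - 81.9 = -9.7 days

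Reading C, complete case and without deduction of the index episode, gives 0 in both.

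**Participants without a value.** Crossover: 0.08 x 315 = 25.2, about 25 per arm. Early deaths after CABG: 0.03 x 315 = 9.5 to 0.05 x 315 = 15.8, about 9 to 16. Early deaths after PCI: 0.048 x 315 = 15.1, about 15. The mortality figures are not split by whether death came before discharge, so these are upper limits for deaths before discharge.

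**The case against.** **The name supplies the cap.** An analyst would probably truncate at 90 and 365 days. That is likely, but the name does not say where the window starts, and columns B and C show that the answer depends on it.

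**The formula hides the CABG index stay.** A reader might infer this, but it holds only under a window from discharge that leaves the index episode out of the deductions. Uncapped, or capped from randomisation, a longer stay lowers the score day for day. A lost arm difference and scores near 1,800 cannot both be charged to the formula, because they come from different readings.

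**Early deaths are dropped, which favours CABG.** A reader might infer this too. Deaths after discharge are counted under every reading. For deaths before discharge, 1.31 identifies deaths through "All-cause mortality (ICD10): (dismeth = 4) OR (a linked record in ONS death registry". This suggests that in-hospital deaths may have a HES discharge record, which would give about 0 instead of no value; that is an inference, not a stated rule. The cited early mortality is also similar for PCI and CABG, so the documents do not show a direction.

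**Early burden is captured elsewhere.** This stands: 1.31, item 3f, collects length of stay, 1.18 collects deaths within 30 days, and overall survival runs from randomisation. DAOH is one of 12 secondary outcomes in the Study Summary and enters neither the primary analysis nor the 414-event calculation. This limits the consequence but does not make the formula usable.

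**Conclusion.** The definition is wrong as written and should be corrected, at the level of a secondary outcome. Three defects need no assumption: there is no cut-off, so the 90- and 365-day outcomes coincide; participants never treated as assigned, or who die waiting, have no starting date, and crossovers strictly have none either; and 1.31 gives a different time point. The lack of a rule for death before index discharge is also plain on the text. Excluding such participants through complete-case handling is a possible consequence and would conflict with intention to treat.

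The difference of about -3 to -10 days that one reading reports as 0 rests on the assumed stays, the absence of readmissions and all early deaths occurring in hospital. It shows how far the readings diverge and does not predict the trial's result. Neither a systematic advantage for CABG nor any effect on the primary conclusion is established.

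**What to change.** Replace the formula in 1.17.2, item 8. Define DAOH-90 and DAOH-365 as the number of days, within 90 and 365 days of randomisation, on which the participant is alive and not an inpatient. State that index and staged stays count as hospital days and that days after death count as 0. The ranges are then 0-90 and 0-365, with a value for every randomised participant whose linked data are available; 1.29 allows withdrawal from linkage, so a value for everyone cannot be guaranteed.

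An elective procedure may fall after day 90 from randomisation, and the 90-day count then contains none of the treatment stay (90 for the day-126 case in column D). Add a supportive count from the procedure date among treated participants, described as not fully intention to treat. For staged PCI, say which procedure date starts that count.

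Reconcile the time points in the Study Summary, 1.17.2 and 1.31, item 3f. The cost is one reworded definition and one extra analysis from HES/ONS and eCRF data already planned. As the trial is open label, make the change before outcome data by arm are examined.
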